9.2.1. Dose Escalation

N-CRM design is a type of Bayesian adaptive dose-escalation approach. The design classifies the DLT rate into four categories and makes dose recommendations based on posterior distribution of the four categories:

- Under-dosing: DLT rate < 16%
- Target toxicity: 16% ≤ DLT rate < 33%
- Excessive toxicity: 33% ≤ DLT rate < 60%
- Unacceptable toxicity: DLT rate ≥ 60%

At the end of DLT observation period for each dose level, the posterior distribution of DLT rate will be summarized by the posterior probability of the DLT rate falling into the interval of under-dosing, target toxicity, excessive toxicity, and unacceptable toxicity respectively. The recommended dose is the one that maximizes the probability of target toxicity while controlling the probability of excessive or unacceptable toxicity no more than 25%.

9.2.1.1. Operating characteristics of the safety stopping rule for VTE events in dose escalation

Simulations were used to evaluate the design performance of the safety stopping rules planned for the safety evaluation of VTE events during the dose escalation phase (Part 1) of this study. In these simulations, we simulate 100,000 independent trials and evaluate the performance of the model on average. In each simulation, a cohort is enrolled until either 2 or more VTE events have been observed among 6 or fewer participants or 3 or more VTE events have been observed among 7-10 participants.

[figure not shown]
[Table 8](#) details the scenarios evaluated as well as the average number of participants dosed in each cohort, and the percentage of simulated trials that completed that dose level. [Figure 4](#) graphically represents the operating characteristics of the safety stopping rules for each cohort. Each line of the plot represents a different true VTE incidence rate detailed in [Table 8](#). The scenarios considered a range from a true VTE incidence rate of 5% to a true VTE incidence rate of 30%. Note that these simulations only take VTE events into consideration, and this VTE safety stopping rule will be evaluated in addition to the traditional DLT rules within the dose escalation framework detailed in [Section 4.1.1](#).

In low VTE incidence scenarios, the cohorts are more likely to fully recruit without stopping early for safety evaluation of the VTE rate. For example, if the true population VTE incidence rate is 5%, only 3.8% of the simulations stopped early for safety, however, if the true population VTE incidence rate is 30%, 69.5% of our simulations stopped early for safety.

Table 8 Simulation scenarios and probability of stopping for VTE safety stopping rule across various true VTE incidence rates

True VTE incidence	% of trials that stopped early for safety
5%	3.8
10%	13.6
15%	26.9
20%	42.1
25%	56.8
30%	69.5

Figure 4 Operating characteristics for the VTE safety stopping criteria

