Number of Participants: It is estimated that up to approximately 60 participants will be enrolled in Part 1. In Part 2, approximately 141 participants will be recruited into Expansion Cohort 2A (~36 participants) and Expansion Cohort 2B (~ 105 participants). Additional tumor-specific cohort(s) and combinations may be added by protocol amendment, based upon emerging pre-clinical data, or clinical data.

Intervention Groups and Duration: In Part 1 of the study, the participants will initially receive GSK3368715 orally. This will include at least one PK/PD cohort and a food effect cohort. The Dose Limiting Toxicity (DLT) period is 21 days, and under protocol amendment 3, there is an addition of a VTE-specific DLT period of 8 (\pm 1) weeks or until study discontinuation whichever occurs sooner. An end of treatment CT image is required if the participant withdraws before the end of the DLT observation period. Alternative dosing schedules and intervention cycles may be investigated. In Part 2, the participants are expected to receive the RP2D established in Part 1. In case of unexpected toxicities, alternative GSK3368715 doses may be explored in Part 2.

The study includes a screening period, an intervention period and follow up. Participants will be screened for eligibility beginning approximately 4 weeks before the start of intervention. Participants with confirmed partial response (PR) or complete response (CR) will be followed for response duration and may be eligible for additional intervention with GSK3368715 at the time of relapse/progression if determined to be deriving clinical benefit in the opinion of the investigator and with approval from the study Medical Monitor.

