 - Upon re-initiation of enrolment under Protocol Amendment 3, details of a VTE meeting the DLT criteria are given in Section 4.1.3 and in Table 6.
- Upon re-initiation of enrolment under Protocol Amendment 3 at 100mg , dose escalation steps will be considered in maximal steps of 50 mg, depending on the pharmacodynamic effects and the safety profile observed in previous cohorts, taking into consideration the updated DLT criteria (see Table 6).
- *Note:* GSK3368715 dose de-escalation is also possible using this method.

An updated posterior estimate of the dose-toxicity curve will also be provided at the time of the dose-escalation meeting. Further details about the N-CRM approach are provided in Section 9. Although the N-CRM will be used to recommend the next dosing level, the DEC (i) will review all available data, including safety, PK and PD data from current and prior cohorts, (ii) can halt or reduce the GSK3368715 dose based on clinical judgement at any time during the trial, and (iii) can recommend alternative schedule(s) if emerging data suggest that continuous daily dosing will result in excessive toxicity or limited efficacy (Section 4.1.4). *Note:* if an alternative schedule is evaluated, the starting dose at the time of a schedule change will be the dose for which the target toxicity level was not exceeded using once daily dosing schedule.

Dose Schedule: GSK3368715 will be dosed initially orally (po) Based on emerging safety-, PK-, and PD- data, the DEC may recommend to evaluate alternative dosing schedule(s). The starting dose for an alternative dosing schedule will not exceed the highest GSK3368715 dose declared safe by the DEC at the time of the proposed schedule change.

During dose escalation, the first dose will be staggered by at least 24 hours between the participants enrolled within a cohort. This staggered dosing start is not required for participants enrolling at previously cleared doses.

PK/PD/Metabolite/Biomarker-Cohort: At GSK3368715 dose levels near to the expected RP2D, the DEC may recommend to expand a cohort(s) to up to 12 participants for additional PK- and PD-, metabolite- and/or biomarker-sample collection.

Under protocol amendment 03, a 100mg PK/PD cohort will be opened on resuming enrolment, and a 50mg PK/PD cohort may be opened in parallel. An additional PK/PD cohort may be opened later at a different dose level. The total maximal number of participants enrolled on PK/PD cohorts will be approximately 30.

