4.1.3. Dose-Limiting Toxicity

All toxicities will be graded using National Cancer Institute – Common Toxicity Criteria for Adverse Events (NCI-CTCAE), version 5.

An AE is considered to be a dose-limiting toxicity (DLT) if the event is considered by the investigator to be clinically relevant and attributed (definitely, probably or possibly) to the study intervention during the first 21 days of intervention and meets at least one of the criteria listed in [Table 6](#).

In addition, there are clear VTE DLT criteria:

- Upon re-initiation of enrolment under Protocol Amendment 3, any cohort in Part 1 with two (2) grade 2 venous thromboembolism (VTE) that requires systemic anticoagulation or \geq grade 3 VTE in up to 6 participants will be considered not cleared and enrolment at this dose level and higher dose levels will be permanently stopped.
- Upon re-initiation of enrolment under Protocol Amendment 3, any cohort in Part 1 with ≥ 3 grade 2 venous thromboembolism (VTE) that requires systemic anticoagulation or Grade ≥ 3 VTEs out of up to 10 participants will be considered not cleared and enrolment at this dose level and higher dose levels will be permanently stopped.
- Upon re-initiation of enrolment under Protocol Amendment 3 at 100mg, dose escalation steps will be considered in maximal steps of 50 mg depending on the pharmacodynamic effects and the safety profile observed in previous cohorts, taking into consideration the updated DLT criteria (see [Table 6](#)).
- Grade 2 venous thromboembolism (VTE) that requires systemic anticoagulation or \geq grade 3 VTE, regardless of investigator assessed causality, will be considered a DLT during the first 8 (± 1) weeks or until study discontinuation (e.g., disease progression), whichever occurs sooner.
- An end of treatment CT image is required if the participant withdraws before the end of the VTE DLT observation period ([Table 6](#)).

If an AE is considered related to the underlying disease it is not defined as a DLT.

Table 6 Dose-Limiting Toxicity Criteria

DLT criteria for Non-hematologic Toxicity	
AST or ALT	
 • Grade 3 • Grade 4 • ALT \geq 5xULN • ALT \geq 3xULN persists for \geq 4 weeks • ALT \geq 3xULN and bilirubin \geq 2xULN (>35% direct bilirubin) • ALT \geq 3xULN and INR >1.5, if INR measured • ALT \geq 3xULN associated with symptoms (new or worsening) believed to be related to liver injury or hypersensitivity

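### Table 8 gives the chance that a cohort is eventually declared not cleared for VTE, not the chance that enrolment is stopped early, because it leaves out the 8-week VTE window

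*Protocol*

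**What the plan says.** **The simulation (Protocol 9.2.1.1).** The rule is simulated in two steps. In the first step, "a cohort is enrolled until either 2 or more VTE events have been observed among 6 or fewer participants". Past the sixth participant the boundary rises by one, and the cohort ends once "3 or more VTE events have been observed among 7-10 participants". On method, the text says that "we simulate 100,000 independent trials and evaluate the performance of the model on average". It gives the range of true VTE rates (5% to 30%), but no accrual rate, time to event or delay before an outcome is known. Stopping early is contrasted with recruiting the cohort in full, and the worked example is that "if the true population VTE incidence rate is 30%, 69.5% of our simulations stopped early for safety". The text also says that Table 8 shows the average number dosed and the percentage completing the dose level. The table in the copy reviewed shows only the percentage stopped early (Figure 4 is not visible).

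**The window (Protocol 4.1.3, Table 6 and Synopsis).** The Synopsis says that "under protocol amendment 3, there is an addition of a VTE-specific DLT period of 8" (in weeks, plus or minus one). Section 4.1.3 sets the same span for a qualifying VTE, "regardless of investigator assessed causality, will be considered a DLT during the first 8" (again in weeks), ending sooner if the participant leaves the study.

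**The two tiers (Protocol 4.1.3, repeated in SAP 2.3).** Two qualifying VTEs in up to 6 participants, or three or more in up to 10, make the cohort not cleared. Enrolment at that dose and above then closes permanently.

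**Spacing (Protocol 4.1.1).** First doses within a cohort are at least 24 hours apart, and "This staggered dosing start is not required for participants enrolling at previously cleared doses". No hold for pending VTE windows within a cohort is stated.

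**Review timing.** Protocol 4.1.4 places the Dose Escalation Committee (DEC) review after the whole cohort has passed the DLT period. Protocol 2.3.1 lists longer VTE monitoring before escalation. SAP 3.1 ties escalation meetings to the first 21 days.

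**The concern.** Cohort stopping rules for VTE are among the mitigations that Protocol 2.3.1 lists for resuming enrolment after the VTE pause, and Table 8 is their only quantified performance. A reader takes from it that a dose with a 30% VTE rate has about a 70% chance of having its cohort cut short. If a VTE can appear up to 8 weeks after the first dose while others are still being dosed, the rule may act only after the cohort is full. It can then still close the dose, but it spares nobody in that cohort.

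A second question follows. If more than six people have been dosed when the second VTE is seen, Section 4.1.3 does not say whether the first tier still applies to the first six or whether only the tier for up to ten is in force.

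**Working it through.** **Inputs.** Boundary, maximum of 10 and Table 8 figures: Protocol 9.2.1.1. Window of 8 weeks: Protocol 4.1.3. Minimum spacing of 24 hours: Protocol 4.1.1. Assumed, because the documents give neither: a fixed accrual gap, and VTE onset uniform over 8 weeks and detected at onset.

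**Step 1: reproduce Table 8.** Let X6 and X4 be the VTE counts in the first six and the next four participants, at true rate p.

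P(cross) = P(X6≥2) + P(X6=1)·P(X4≥2) + P(X6=0)·P(X4≥3)

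At p = 0.30: 0.5798 + 0.3025×0.3483 + 0.1176×0.0837 = 0.5798 + 0.1054 + 0.0098 = 0.695.

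| True VTE rate | 5% | 10% | 15% | 20% | 25% | 30% |
|---|---|---|---|---|---|---|
| Table 8 (%) | 3.8 | 13.6 | 26.9 | 42.1 | 56.8 | 69.5 |
| Exact (%) | 3.6 | 13.5 | 27.2 | 42.3 | 56.8 | 69.5 |

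All six agree within 0.3 points. The formula is the probability of at least 2 in the first 6 or at least 3 in 10. It contains no time, so it is the chance that the cohort is eventually not cleared, counted in enrolment order.

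**Step 2: crossings that spare nobody.** Some crossings occur at the tenth participant. At p = 0.30:

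[P(X6=1)·P(X3=1) + P(X6=0)·P(X3=2)]×0.30 = [0.3025×0.441 + 0.1176×0.189]×0.30 = 0.047,

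where X3 is the count in participants 7 to 9. So 69.5 − 4.7 = 64.8% stop before the tenth, even with instant outcomes (mean dosed 6.5).

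**Step 3: add the delay.** Participant i is dosed at (i−1)×gap and has a VTE with probability p at a uniform time in the next 8 weeks. The boundary time is the earlier of the second VTE among the first six and the third among ten. 100,000 cohorts were simulated per row, so the standard error is at most √(0.25/100,000) = 0.16 points.

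| Accrual | Stopped before 10th, p=20% | Stopped before 10th, p=30% | Mean dosed, p=30% |
|---|---|---|---|
| Instant outcomes | 38.8% | 64.8% | 6.5 |
| 1 per 4 weeks | 37% | 63% | 6.8 |
| 1 per 2 weeks | 36% | 59–60% | 7.4 |
| 1 per week | 24% | 44% | 8.6 |
| 2 per week | 8% | 16% | 9.5 |
| 1 per day | 1% | 2% | 10.0 |

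The chance of crossing the boundary stays at about 42% and 70% in every row. If VTEs are detected only at 8 weeks, the one-per-week figures fall to 4% and 9%.

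**Step 4: the two tiers.** Suppose the first tier lapses once all ten are dosed, so that only 3 or more of 10 counts. The two readings differ only where X6 = 2 and X4 = 0. At p = 0.30 that is 0.3241×0.2401 = 7.8%.

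| True VTE rate | 10% | 20% | 30% |
|---|---|---|---|
| Not cleared, enrolment order | 13.5% | 42.3% | 69.5% |
| Not cleared, 3 or more of 10 only | 7.0% | 32.2% | 61.7% |
| Cohorts where the readings differ | 6.5% | 10.1% | 7.8% |

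**The case against.** **Table 8 is numerically right for a meaningful quantity.** A reader might infer that its figures hold only if each outcome is known before the next participant is dosed. That is not so: counted in enrolment order, the not-cleared probability is unaffected by delay. The consequence in Section 4.1.3, closing that dose and higher ones, protects later participants even when the cohort is already full. This stands. It does not rescue the label, because Section 9.2.1.1 describes enrolment ending and contrasts that with full recruitment.

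**The loss depends on accrual.** At one participant per 2 to 4 weeks it is modest. The documents offer only a rough clue: 19 participants had been dosed by Amendment 3, dated 5 December 2019. If the first dose fell between 2 May 2018 and 22 February 2019 (assumed), that is 83 to 41 weeks, or one per 4.4 to 2.2 weeks across the study. The pause and any clustering are unknown, so this cannot settle the rate within a cohort.

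**There are other gates.** The 24 hours is a minimum. Initial cohorts hold up to three, with expansion at the DEC's discretion, and the DEC may halt any cohort at any time. So a reader should not conclude that enrolment is never paused; the documents simply state no pause. These gates are discretionary, or act between dose levels, and none is in the simulation.

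**The tiers may not conflict.** Each is written as sufficient on its own, and nothing says that 2 of 10 reverses an earlier crossing. The wording is open rather than contradictory, and 61.7% is the result on one reading.

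**Enrolment has ended.** SAP 2.1 reports that the 100 mg cohort was deemed safe and that no more participants will be enrolled. That lowers the priority but does not make the label correct.

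**Conclusion.** The concern holds in a limited form. Table 8 is correct as the probability that a cohort is not cleared, counted in enrolment order, and is mislabelled as the probability of stopping early. At a true VTE rate of 30% the early-stopping figure is 64.8% rather than 69.5% before any delay is considered. It is about 63% at one participant per 4 weeks, 44% at one per week and 16% at two per week. Those delayed figures rest on assumed uniform onset over 8 weeks, detection at onset, fixed accrual gaps and counting in enrolment order. The 64.8% rests on none of the timing assumptions.

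A reader might go further and say that the stated safety performance is not delivered. The documents do not support that: they give no accrual rate, the dose-closing consequence survives the delay, and the DEC can halt a cohort. The supported statement is that sparing participants within the cohort is not assured.

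The open counting rule is a separate matter that does not depend on onset timing. It moves the not-cleared probability by 6.5 to 10.1 points at true rates of 10% to 30%. Overall this should be fixed, but it is not critical.

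**What to change.** - **Relabel** the Table 8 column as the percentage of cohorts not cleared, and state the counting rule behind it (first six, then up to ten, in enrolment order).
- **Re-run** the simulation with the 8-week lag over a stated range of accrual rates and onset patterns. Add the percentage stopped before the last participant is dosed and the average number dosed, which the text already says the table gives.
- **Reconcile the two tiers** in Protocol 4.1.3 and SAP 2.3 with the rule that was simulated, saying whom each tier counts once more than six have been dosed.
- **Reconcile the 21-day escalation gate** in SAP 3.1 with the 8-week VTE window.

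Which threshold applies, and whether enrolment should wait for pending windows, are clinical decisions for the sponsor. The request is only that the text and the simulation describe the same rule.

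The cost is a short re-simulation and a few sentences. The early-stopping figures will look less favourable. With enrolment closed, no planned analysis changes; the gain is an accurate account of the rule under which Part 1 resumed.

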9.2.2. Dose Expansion

Part 2A DLBCL Cohort

ORR will be analyzed using a Bayesian hierarchical model that allows information borrowing between MTAP proficient and MTAP deficient subgroups within the DLBCL cohort. An MTAP defined subgroup will be considered as effective at the end of study if the posterior probability of ORR>10% is more than 85%. In this design, up to 30 participants will be enrolled into each MTAP defined subgroup and up to 36 will be

enrolled for the entire cohort. The simulation results assuming 50:50 ratio between MTAP proficient participants and MTAP deficient participants are displayed in [Table 9](#).

Assume $\pi_g = \Pr(\text{response} \mid \text{intervention, group } g)$ denote the probability of response for group g participants, where group g represents MTAP proficient subgroup or MTAP deficient subgroup, and $\pi = \Pr(\text{response} \mid \text{intervention})$ denote the probability of response for the entire cohort. Let $\theta_g + R_g$ be the logit of the group g response rate, $\theta_{AG} + R_g$ be the logit of the cohort response rate, i.e.,

$$\theta_g + R_g = \log\left(\frac{\pi_g}{1 - \pi_g}\right).$$

and

$$\theta_{AG} + R_g = \log\left(\frac{\pi}{1 - \pi}\right).$$

The hierarchical model assumes

$$\theta_g \sim N(\mu, \tau^2),$$

The prior distributions for μ , τ^2 and θ_{AG} are defined as follows:

$$\begin{aligned}\mu &\sim N(-2.2, 6.9), \\ \tau^2 &\sim IG(1, 47.61), \\ \theta_{AG} &\sim N(-2.2, 6.9).\end{aligned}$$

where $IG(\alpha, \beta)$ is the inverse gamma distribution defined by:

$$f(x|\alpha, \beta) = \frac{\beta^\alpha e^{-\beta/x}}{x^{\alpha+1}\Gamma(\alpha)}.$$

These choices of α and β correspond to a mean weight parameterization with mean 6.9 and weight 2. The prior for μ and θ_{AG} centers the response rate at 10% (the assumed underlying control rate).

Table 9 Design Characteristics for Bayesian Hierarchical Design for Part 2A DLBCL Cohorts

Scenarios for ORR	Proportion of MTAP- group meeting success criteria	Proportion of MTAP+ group meeting success criteria
0.3 in MTAP-; 0.3 in MTAP+	81.3%	81.7%
0.1 in MTAP-; 0.1 in MTAP+	8.3%	8.2%
0.3 in MTAP-; 0.1 in MTAP+	80.4%	10.3%

*The results are based on 5000 simulations with interim futility analysis starting after at least five participants in each subgroup and being done every 12 weeks.

Part 2B Solid Tumor Cohorts

The primary endpoint of ORR will be assessed for each of the two MTAP defined subgroups (MTAP proficient and MTAP deficient) within each of the three solid tumor cohorts in Part 2B. The primary analysis of ORR for each tumor cohort and MTAP defined subgroup is based on a Bayesian hierarchical model. The Bayesian hierarchical model will allow information borrowing across the three different cohorts as well as between MTAP proficient and MTAP deficient subgroups. The models focuses more on the MTAP- subgroups than MTAP+ subgroups. It borrows more across MTAP- subgroups compared to MTAP+ subgroups when treatment works across MTAP- subgroups and MTAP+ subgroups. An MTAP defined subgroup within one cohort will be considered as effective at the end of study if the posterior probability of $ORR > 10\%$ is more than 94%. Up to 35 participants will be enrolled into one disease specific cohort.

The simulation results under the scenario of 50:50 ratio between MTAP proficient participants and MTAP deficient participants are displayed in [Table 10](#). The design has been simulated under nine scenarios for the true distribution of ORR effects across tumor cohort and MTAP defined subgroups. The probability of declaring effective for each subgroup within each disease specific cohort is provided. Additionally, the proportion of trials that correctly detect all effective subgroups (ignoring the design decisions for any ineffective subgroups) is provided.

Table 10 Design Characteristics for Bayesian Hierarchical Design for Part 2B Solid Tumor Cohorts

	Pancreatic		NSCLC		Bladder	
	ORR in truth					
	MTAP-	MTAP+	MTAP-	MTAP+	MTAP-	MTAP+
All Null	10%	10%	10%	10%	10%	10%
All effective	30%	30%	30%	30%	30%	30%
2 Eff in all comers	30%	30%	30%	30%	10%	10%
1 Eff in all comers	30%	30%	10%	10%	10%	10%
All Eff in MTAP-	30%	10%	30%	10%	30%	10%
2 Eff in MTAP-	30%	10%	30%	10%	10%	10%
1 Eff in MTAP-	30%	10%	10%	10%	10%	10%
1 Eff in all comers, 2 Eff in MTAP-	30%	30%	30%	10%	30%	10%
1 Eff in all comers, 1 Eff in MTAP-	30%	30%	30%	10%	10%	10%

	Pancreatic		NSCLC		Bladder	
	Proportion of trials declaring efficacy (Power or Type I error)					
All Null	0.015	0.021	0.025	0.031	0.023	0.031
All effective	0.904	0.838	0.914	0.831	0.913	0.831
2 Eff in all comers	0.817	0.758	0.812	0.783	0.117	0.074
1 Eff in all comers	0.631	0.688	0.066	0.051	0.068	0.055
All Eff in MTAP-	0.903	0.032	0.890	0.026	0.890	0.033
2 Eff in MTAP-	0.737	0.028	0.738	0.042	0.209	0.022
1 Eff in MTAP-	0.571	0.047	0.093	0.016	0.090	0.021
1 Eff in all comers, 2 Eff in MTAP-	0.934	0.595	0.851	0.067	0.857	0.072
1 Eff in all comers, 1 Eff in MTAP-	0.842	0.639	0.730	0.090	0.184	0.040
	Proportion of trials picking all the effective subgroups correctly					
All Null	NA					
All effective	0.535					
2 Eff in all comers	0.472					
1 Eff in all comers	0.459					
All Eff in MTAP-	0.777					
2 Eff in MTAP-	0.614					
1 Eff in MTAP-	0.571					
1 Eff in all comers, 2 Eff in MTAP-	0.435					
1 Eff in all comers, 1 Eff in MTAP-	0.440					

